- g. Active use of the System will be observed by a Technical Observer, i.e., an IRB-approved member of the investigative team. The Observer will generally observe the system continuously, with a minimum of at least one observation every 15 minutes. These observations provide additional assurance that there is no potential interference with any other aspect of the patient's care; that the technical performance of the System is grossly consistent with its intended operation; to ensure that the patient doesn't express any concern; and to ensure that the nurse doesn't express any concern. By protocol, if the nurse, patient, or patient family member states any negative perception of the investigational system, the Technical Observer will ask whether the nurse/patient/family member prefers the protocol to stop, and will oblige if this is requested. If the protocol is stopped early by request of the nurse, patient, or family member, the Technical Observer will ask for feedback after stopping the protocol and removing the apparatus: "You requested that we stop our testing protocol. Can you tell us why, to help us ensure that this testing protocol is safe and appropriate for other ICU patients?" The protocol will also terminate early if an Exclusion criterion is met: receiving two simultaneous vasopressors running at maximum doses (per the ICUs own protocols) or who is on one maximum-dose vasopressor and has a contraindication to receiving a second vasopressor (e.g., insufficient vascular access). During the protocol, the nurse will have the option to adjust the Index Threshold per their clinical practice preferences, and the Technical Observer will provide technical support of the nurse decides to do this. Lower thresholds for the Index Threshold provide higher sensitivity and earlier warnings at the expense of reduced positive predictive value. Higher thresholds the Index Threshold provide lower sensitivity and less advanced notifications at the benefit of

higher positive predictive value. Within the second hour of the protocol session, the Technical Observer will explicitly confer with the nurse about the operation of the system, confirming whether the nurse understands the visual display elements, whether the nurse would like to adjust the Index Threshold, and whether the nurse has any concerns about the investigational display or the protocol. This check-in will occur at a time when the nurse is not occupied with direct patient care.

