- h. As well the research staff member will ensure that the nurse adjusts the investigational system's MAP and SBP goals, if these are ordered to be changed during the protocol.
 - i. The Technical Observer will document any identifiable interventions of events that have any effect on the patient's blood pressure or heart rate. When the Technical Observer perceives any substantial changes in the subject's hemodynamics, a time-stamped annotation will be made for the perceived cause. The goal is to have these events documented with very precise temporal resolution, i.e., down to the precise minute that the events occur. The Technical Observer may ask the nurse to clarify what intervention is occurring; by protocol, Technical Observer will not ask this clarification if there is any perception that time-sensitive interactions being delivered and/or if the nurse is discussing patient management with any other clinical team member. The Technical Observer will never suggest intervention or recommend any clinical care for the patient.
 - j. If the primary nurse-subject (who provided consent) takes a break and there is a temporary substitute nurse, we will turn off the display so that the investigational software cannot affect decision-making (except if the substitute nurse has been a nurse-subject for this study for a different ICU patient having completed the full protocol within the past 30 days; under that condition, we will continue the protocol during the break). If the primary nurse-subject break lasts longer than 60 min, we will terminate that enrollment.
 - k. The investigational software will be terminated one hour before the Technical Observer is scheduled to depart for the day, or one hour before the end of the consenting nurse's shift, or a maximum of 8 hours (whichever is shorter). After each subject enrollment, the apparatus will be removed from the care area and cleaned with an antibacterial wipe. The System hardware will be inspected to ensure there are no visible abnormalities such as evidence of spills or physical damage.

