- l. All ICU clinicians, including physicians, RN, NPs, and PAs, will be educated about the study by email. The "investigational protocol information" document will be sent to all clinicians in the department at least every 6 months. Before any new enrollments, we will confer with the ICU director whether there are new clinicians working since the last enrollment who need to be emailed (i.e., new staff or residents starting their ICU clinical rotation).

Data to be collected and when the data is to be collected

Subjects will be enrolled during periods when the study staff are available to conduct the protocol for a minimum of four hours of data collection (plus an extra hour for apparatus cleaning as well as conducting the post-enrollment clinician survey). The maximum duration of data collection for a given subject will be eight hours, i.e., the duration of a shift for the study staff.

During data collection, the System will automatically archive the subject's vital signs through time. The system will also auto-log any abnormal functionality.

The technical observer will annotate any clinical interventions; any technical abnormality observed in System operation; and any concerns by the clinical staff or the patient or the patient's family. The technical observer will also provide subjective descriptions of the patient's apparent state (for purposes of better understanding retrospective data analysis after the study is complete).

In the final hour of each data collection session, we will ask the nurse to complete a brief questionnaire that provides specific feedback and also indicates whether performance of the investigational system was generally acceptable (see below). This will conclude data collection.

“Thank you for participating in the clinical testing of our decision-support system. We would like your final feedback about the following topics.”

- Question 1: Do you agree or disagree with the following statement:

“This system will make it generally easier to keep blood pressure within the goal range during continuous vasopressor infusion?”

 - 1- Strongly disagree
 - 2- Disagree
 - 3- Neutral
 - 4- Agree
 - 5- Strongly agree
- Question 2: What feature(s) of the system do you think will be most useful, either to yourself or to other typical ICU caregivers?
- Question 3A: Did you identify any display output by the system that is confusing, or inaccurate?
- Question 3B (if answer “yes” to 3A): If so, what?

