- Question 3C (if answer “yes” to 3A): Do you perceive that the confusing or inaccurate display output could possibly lead to any patient management error?
- Question 4A: This system provides lots of visual information, which might be distracting. At any time, did the system actually distract you from noticing something important about your patient or administering important care to your patient, such that your response to the patient was delayed?
- Question 4B (if answer “yes” to 4A): If so, what?
- Question 5: Any other ideas about what could be improved, and how?
- Question 6: If we want to hold a catered lunchtime focus group to discuss possible modifications to the system, would you be willing to join for 20 minutes, so we can get your feedback?

P.6 BIOSTATISTICAL ANALYSIS

Specific data variables being collected for the study

- Survey results from clinicians
- Annotation of any technical issues observed by Technical Observer
- System database archive of measured vital-signs and associated vital-sign forecasts
- Any error- and critical-level log statements from the server log file
- Any error- and critical-level log statements from the UI log file

Study endpoints

Subjects will be enrolled during periods when the study staff are available to conduct the protocol for a minimum of four hours of data collection (plus an extra hour for apparatus cleaning as well as conducting the post-enrollment clinician survey). The maximum duration of data collection for a given subject will be eight hours, i.e., the duration of a shift for the study staff.

Statistical methods

There will be two aspects to the data analysis: “clinician perceptions” and “technical operation”.

For the clinician perception, we will pool the feedback results from Questions 1-4. We will report quantitative responses for Questions 1, 3A, 3C, and 4A.

For Questions 2, 3B, 4B, and 5, we will employ an “exploratory sequential mixed methods design” whereby we use the results of the questionnaires to form variables that represent the most common qualitative answers, then code the questionnaire responses according to those variables, yielding quantitative results for the user perception survey data, to supplement the free-text feedback.

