4. Ensure that the data reported in REDCap from each nursing-subject interview are complete.
5. Ensure that the log files for each patient-subject session do not include any error- or critical-level message (except for those that are expected to naturally occur during system shut-down, which would be after each patient-subject data collection session has been completed).
6. Ensure that any event note for the patient's ICU documentation record that involved more than the primary nurse as a clinical responder was captured by the Technical Observer's annotations.

Safety monitoring

After the first 5 subjects are enrolled, the nurse-subject responses to the questionnaire will be submitted to the IRB, along with a report of any adverse events.

The following events represent possible adverse events:

- (a) the Technical Observer (a member of the research team) identifies any failure of the software and terminates the session (the Technical Observer may also terminate for any subject reason related to any subjective perceived negative impact on the subject's care);
- (b) if the nurse indicated that the protocol was having any negative effect on the patient's care, either during the execution of the protocol session, or in responses to the questionnaire that is conducted after every enrollment ("Question 3: Did you identify any output by the system that is dangerously confusing, or dangerously inaccurate? If so, what?"; and "Question 4: This system provides lots of visual information, which might be distracting. At any time, did the system actually distract you from noticing something important about your patient or administering important care to your patient, such that your response to the patient was delayed?");
- (c) if the patient/close family member indicated any discomfort with the protocol session.
- (d) Review of the software logs indicates any error-level or critical-level log statements were generated.

(e) Review of the software data archive indicates any interruption in the routine monitoring of vital-signs.

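### Does the early-stop question in P.5 replace the nurse questionnaire and so bias the pooled survey upward?

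*Combined protocol and SAP*

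**What the plan says.** P.5 Study Procedures, step g, covers sessions that someone asks to end. After any negative remark about the system, "the Technical Observer will ask whether the nurse/patient/family member prefers the protocol to stop, and will oblige if this is requested". Then: "If the protocol is stopped early by request of the nurse, patient, or family member, the Technical Observer will ask for feedback after stopping". The scripted question asks why they stopped, so that the team can judge whether testing is safe and appropriate for other ICU patients.

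Two further routes to an early end appear in P.5. Step g adds: "The protocol will also terminate early if an Exclusion criterion is met". Step j adds: "If the primary nurse-subject break lasts longer than 60 min, we will terminate that enrollment". P.9, Safety monitoring, item (a), also lets the Technical Observer end a session.

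The questionnaire is described in three places:

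- P.5, Data to be collected: "In the final hour of each data collection session, we will ask the nurse to complete a brief questionnaire".
- P.9, Safety monitoring, item (b), refers to a nurse reporting harm to care "in responses to the questionnaire that is conducted after every enrollment".
- P.9, Independent monitoring of source data, item F.4: "Ensure that the data reported in REDCap from each nursing-subject interview are complete".

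The analysis is in P.6, Statistical methods: "For the clinician perception, we will pool the feedback results from Questions 1-4". Quantitative responses are reported for Questions 1, 3A, 3C and 4A. No denominator and no rule for a missing questionnaire are given, and there is no acceptance threshold or test.

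**The concern.** The questionnaire is timed to the last hour of a session, and the only feedback step written next to a requested stop is a different question. A reader of step g alone could conclude that the nurse is asked why and nothing else. A nurse's criticism is also what prompts the offer to stop, so any questionnaire lost this way would be lost because of the opinion it measures.

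The sole specific aim in P.2 is candid feedback on the value of the system, and P.8 says the results will be used to test acceptability. P.1 discloses that the investigators invented the software and may gain financially. If the least satisfied nurses were missing, agreement on Question 1 would be too high and the rates of confusion and distraction (Questions 3A, 3C and 4A) too low. Each lost questionnaire might also seem to weaken the 98% detection claim that supports the 20 sessions.

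**Working it through.** **1. Does the text remove the questionnaire after an early stop?**

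| Place | Who is asked | When | Exception for early stops |
|---|---|---|---|
| P.5 step g, reason for stopping | Nurse, patient or family member who asked to stop | After the apparatus is removed | Applies only to requested stops; does not mention the questionnaire |
| P.5, Data to be collected | The nurse | Final hour of each session | None |
| P.9, Safety monitoring (b) | The nurse | After every enrollment | None |
| P.9, item F.4 | Monitor checks each nurse interview | After every 5 subjects or each quarter | None |

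The step g question cannot be a general substitute, because it may go to a patient or relative who would never receive the nurse questionnaire. Its stated purpose is safety for later patients. The two statements on when the questionnaire is given cover all sessions and all enrollments. Step k and the data-collection section place the survey in a wrap-up hour after the software is switched off, and such a step can also follow an early end. On this reading the number of missing surveys is k = 0.

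**2. Bias if surveys were skipped after all**

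Inputs: 20 sessions (P.6, Power analysis); k missing surveys and completers' agreement rate c, both assumed because the documents give neither. Worst case: every missing nurse would not have agreed.

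- Reported rate: c = a/(20 − k), where a is the number agreeing.
- Rate over all 20: a/20 = c(20 − k)/20.
- Overstatement: c − c(20 − k)/20 = c·k/20.

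| k | c | Reported | Over all 20 | Overstatement |
|---|---|---|---|---|
| 0 | any | c | c | 0 |
| 1 | 0.80 | 80% | 76% | 4 points |
| 2 | 15/18 | 83% | 75% | 8 points |
| 3 | 14/17 | 82% | 70% | 12 points |
| 4 | 12/16 | 75% | 60% | 15 points |

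For k = 3 the exact 95% intervals are 57-96% (14/17) and 46-88% (14/20), which overlap widely. Every non-zero row scores every stop as not agreeing, including any caused by the patient, the family, the exclusion rule or a long break.

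**3. How likely is any early stop?**

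With an assumed stop rate q per session, the chance of at least one in 20 is 1 − (1 − q)^20: 33% at q = 2%, 64% at 5% and 88% at 10%. Early stops may well occur, so the handling is worth understanding, but a stop is not the same as a missing survey.

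**4. The 98% figure**

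The plan takes 98% at 20 users from an outside source and gives no per-user detection probability, so it cannot be reproduced. Calibrating the usual discovery model 1 − (1 − p)^n to it gives p = 1 − 0.02^(1/20) = 0.178. Then n = 17 gives 96.4% and n = 15 gives 94.7%. Losing a few surveys changes little, provided the loss is unrelated to the problems found. P.3 also lets a nurse take part more than once, so a session is not necessarily a separate user.

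**The case for a change.** The strongest case for a change is that step g is the specific instruction staff will have in hand after a stop, while the statements covering each session and every enrollment are general. The monitor's item F.4 checks interviews for completeness but does not expressly require one for every started session. Even if the questionnaire is always offered, a nurse who has just asked to stop may decline, and P.6 has no rule for that. Since criticism triggers the offer to stop and the investigators have a financial interest, an open denominator deserves attention.

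Part of this stands. No sentence says how a survey timed to the final hour works when the session is cut short, or whether such a session counts among the 20 or in the pooled results. If a nurse-requested stop did lose a survey, the loss would probably be informative and favour the system.

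The rest does not stand. A specific instruction that adds a question does not cancel a general one that applies to every session. Nor would the opinion vanish if a questionnaire were missed. The Technical Observer annotates concerns of the clinical staff, step g has a second-hour check with the nurse, and the stopping question records the reason. Under P.9, a nurse's report of a negative effect on care, made during the session or in the questionnaire, is a possible adverse event to be assessed within 5 days. Stops by the patient, the family, the exclusion rule or a long break need not reflect the nurse's view, so treating them all as dissatisfied users is too broad.

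**Conclusion.** The concern does not hold as a defect in the plan. Nothing in the protocol replaces the questionnaire with the stopping question, and two statements make the questionnaire universal. Followed as written, the plan loses no survey and the bias is zero. The 8 to 15 points for two to four stops are correct arithmetic, but they are a worst case on assumed stop counts and agreement rates and require surveys to be skipped contrary to P.5 and P.9.

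The remaining gap concerns timing and counting after an early end. The survey summary is descriptive, covers 20 sessions and has no threshold or test, so no decision rule turns on the denominator. An analyst would naturally report sessions started, early stops by reason and questionnaires completed beside Question 1, and the protocol already collects or logs what that needs. This conclusion assumes that staff follow the each-session and every-enrollment wording.

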Note the conflict of interest (COI) which is also found in the consent form: "Investigators on this study invented the software that is used in this study. The hospital owns this software and therefore the investigators and the hospital may benefit financially if this study shows that the technology is valuable. The hospital's conflict of interest policies are handled by the hospital's owner, Partners HealthCare. In accordance with these policies, Partners has determined that the interests create no significant risk to the welfare of participants in this study or to the integrity of the research. If you want more information

about this, please contact the Partners Office for Interactions with Industry at [contact], [contact].”

P.2 SPECIFIC AIMS

Specify objectives and hypotheses to be tested in the research project

This is a live test of a decision-support system. The specific aim is to obtain candid user feedback about perceptions of the value of the automated decision-support.

P.3 SUBJECT SELECTION

This will be a convenience sample of 20 individual patient-subjects and also the 20 nurse-subjects who correspond to the primary nurses managing the patient-subjects. Note: patient-subjects will all be unique. Given the limits of the size of the ICU nursing staff, any nursing-subject may participate multiple times (we will seek to maximize the number of different nurse-subjects as described below).

Inclusion/exclusion criteria

Inclusion

1. Adult patient (18 years or older) receiving continuous vasopressor infusion to maintain blood pressure;
2. Clinician treating patient estimates future duration of vasopressor infusion likely at least 4 additional hours;
3. Provider order has been made that sets lower limit for mean arterial pressure;
4. Indwelling arterial catheter has been placed for continuous blood pressure monitoring.

Exclusion

1. Lack of consent or at the discretion of the patient’s primary nurse;
2. The discretion of any of the patient’s other clinical providers;
3. People who do not speak English will be excluded. The rationale is that this protocol involves the bedside deployment of an investigational system plus longitudinal observation. Our mitigation for psychosocial risk involves a continual observer who can monitor for any evidence of subject psychosocial discomfort, which involves the ability to effectively communicate with the subject throughout the duration of the protocol. This therefore excludes patients who do not speak English.

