According to the FDA “Since the parameters needed to determine sample size cannot be estimated easily or cannot be estimated at all prior to testing, a sample of 15 people to detect most of the problems in a user interface constitutes a practical minimum number of participants for human factors validation testing [4 on Section P.10].

Faulkner et al. [5 on Section P.10] estimated that a sample size of 20 users is sufficient to find an average of 98% of human use factor design failures; this is the basis of our plan to conduct 20 test sessions.

P.7 RISKS AND DISCOMFORTS

The System is only intended for use for investigational purposes. It is a secondary display and does not replace any device in current use. Therefore, risks may be accepted if they do not pose greater risk than usual care. When an identified risk is potentially worse than usual care, then reasonable risk mitigation is employed. Risk assessment and risk mitigation were developed and reviewed by a collaborative team including engineers with expertise in medical software and physicians.

Risks and discomforts are documented and assessed in detail in Section 4 of this IDE Application.

Complications of surgical and non-surgical procedures

N/A

Drug side effects and toxicities

N/A

Device complications/malfunctions

Device risks are documented and assessed in detail in Section 4 of this IDE Application.

Psychosocial (non-medical) risks

For PHI, identifiable health information will be stored on a computer on the Partners network with password protections enabled and anti-virus software or an encrypted laptop and access to identifiable data will be limited to study staff by use of password protected files or restricted shared file areas. Name and/or medical record number will be replaced with a study ID or code and the key to the code stored in a separate password RedCap project. Direct identifiers, such as name and medical record number, will be removed once all of the data is collected and analysis performed on de-identified data.

See Section 4 of this IDE Application for additional consideration of psychosocial risk.

Radiation risks

N/A

P.8 POTENTIAL BENEFITS

Potential benefits to participating individuals

We cannot guarantee there will be benefits. The investigational software system has the potential to improve BP management in the patient-subjects.

Potential benefits to society

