We will use the results of the study to test that the investigational system is acceptable for clinical use by clinical users. This will help establish that the system is suitable for clinical use in a future investigation (user feedback from this trial will also be incorporated to further enhance the systems). Ultimately, this investigation will be a key step in developing a new tool with the potential to promote tight blood pressure control in critically-ill patients.

P.9 MONITORING AND QUALITY ASSURANCE

To ensure high quality protocol compliance, all study members who serve as Technical Observers will review the study protocol and sign a written acknowledgement that the protocol was reviewed. Prior to conducting the trial, Technical Observers will have had at least 250 hours working in a hospital or medical environment in a capacity that involves patient interaction, including as a medical scribe or emergency medical services.

“Protocol trainee” will refer to a study team member who has not completed protocol training. The trainee will observe a trained study team member conduct the protocol for one session (the PI will conduct the protocol for at least the first subject). Then the trainee will be considered trained. The PI will be available by text or cellphone at all times during an active data collection session.

Independent monitoring of source data

We will employ an independent monitor, [name], who is qualified as an experienced research manager and who has been an investigator and/or monitor for prior investigations that required compliance with FDA regulation.

The completeness of the following **study files** will be verified on a bi-annual basis:

A. Mass General Brigham (MGB) Human Research Committee (IRB):

1. All IRB Correspondence is on file
2. The study staff are IRB approved prior to performing any study procedures
3. Adverse events and deviations are reported to IRB per current guidelines
4. All versions of the IRB protocols and informed consent forms are on file
5. IRB is duly constituted and complies with applicable local and national laws and regulations in countries, including protections against conflicts of interest
6. Compliance with the institution's research information security office guidance has been maintained

B. FDA

1. All FDA correspondence (amendments, safety reports, annual review) is on file
2. Documentation of serious adverse events that are unexpected and related are reported to FDA within 7 calendar days

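### The protocol says the nurse questionnaire shows whether the system is acceptable, but no question asks this and no measure of it is named; P.6 also plans no count of sessions stopped early

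*Combined protocol and SAP*

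**What the plan says.** **Purpose.** The aim in P.2 is to "obtain candid user feedback about perceptions of the value of the automated decision-support". P.5 (Data to be collected) goes further and says that the questionnaire, besides giving specific feedback, "indicates whether performance of the investigational system was generally acceptable (see below". P.8 (Potential benefits to society) says the results will be used "to test that the investigational system is acceptable for clinical use by clinical users", and adds: "This will help establish that the system is suitable for clinical use in a future investigation".

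**Endpoints and analysis.** Under Study endpoints, P.6 begins "Subjects will be enrolled during periods when the study staff are available to conduct the protocol" and continues only with session length. Statistical methods pools Questions 1 to 4 as clinician perception and states: "We will report quantitative responses for Questions 1, 3A, 3C, and 4A". Free-text answers to Questions 2, 3B, 4B and 5 are to be coded into categories. The sample size rests on finding design problems in a user interface: "this is the basis of our plan to conduct 20 test sessions".

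**Early stops.** Under P.5 step g, a nurse, patient or family member may ask to stop. The Technical Observer then asks: "You requested that we stop our testing protocol. Can you tell us why". A session can also end because an exclusion criterion is met (step g), because the nurse's break exceeds 60 minutes (step j), or because the Technical Observer terminates it (P.9, Safety monitoring). P.6 lists no summary of any of these.

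**The concern.** The protocol attributes to the questionnaire a property that the questionnaire does not have. If the report is to say whether the system was acceptable, someone must decide after the fact which answers count. Agreement on Question 1, absence of a yes to 3C and absence of a yes to 4A could each be put forward, alone or together, and nothing in the plan chooses between them. The conflict-of-interest note in P.1 discloses that investigators invented the software and that they and the hospital may benefit financially if it is shown to be valuable. The same note records the institution's view that this poses no significant risk to the integrity of the research. The disclosed interest is still a good reason to fix the measure beforehand.

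A judgement that was never asked for also cannot be recovered once the sessions are over.

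A request to stop is direct evidence on acceptability. Under the present P.6, nothing commits the authors to show how many sessions ended that way next to the perception results.

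**Working it through.** No arithmetic on trial data applies. The one numerical rationale in P.6, that 20 users find on average 98% of design failures, comes from a cited study. It cannot be reproduced from the protocol's own inputs, and this point does not depend on it. The check sets the acceptability statement against the instrument and the analysis plan.

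**Step 1: the questionnaire (P.5) against its planned use (P.6).**

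| Item | Subject | Use in P.6 |
|---|---|---|
| 1 | Whether the system eases BP control (5-point) | reported quantitatively |
| 2 | Most useful features | coded from free text |
| 3A | Any confusing or inaccurate display | reported quantitatively |
| 3B | What it was | coded from free text |
| 3C | Whether it could lead to an error | reported quantitatively |
| 4A | Whether distraction delayed a response | reported quantitatively |
| 4B | What happened | coded from free text |
| 5 | Ideas for improvement | coded from free text |
| 6 | Willingness to join a focus group | none stated |

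The count is 4 reported + 4 coded + 1 with no stated use = 9 parts. Parts that ask whether performance was acceptable: 0 of 9. Items 1, 3A, 3C and 4A are related to acceptability, but none is designated as its measure.

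**Step 2: whether P.6 supplies a combination.** It pools Questions 1 to 4 without giving a pooling rule or cut-off, and does not link the pool to acceptability.

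**Step 3: whether Study endpoints supplies one.** It repeats the P.5 paragraph on staff availability and the four-to-eight-hour session. The text is present and readable, so this is neither redaction nor a conversion fault.

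**Step 4: whether P.9 supplies one.** A nurse's report of a negative effect on care, including through Questions 3 and 4, is a possible adverse event. It is assessed within 5 days, and any one of three named roles can halt the study. Questionnaire responses also go to the IRB after the first 5 subjects. This deals with individual unfavourable answers and does not define overall acceptability. (P.9 also words Question 3 more narrowly than P.5 does, asking about dangerous confusion or inaccuracy.)

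**Step 5: early stops.** Requests and reasons are collected (P.5 step g), and several kinds of stop can reach safety review (P.9). The analysis in P.6 covers survey items, technical operation, time in BP range, prediction error and subject characteristics. Early stops are not among them.

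**The case against.** The strongest reply is that this is a 20-session descriptive usability test. P.6 promises no acceptability percentage, cut-off or hypothesis test. Every closed item that bears on acceptability is to be reported, so readers can see each one and selective use is limited. The P.8 sentence is a statement of societal benefit, hedged as helping to establish suitability. P.9 already acts on adverse answers. The Study endpoints heading looks misfilled, and the heading after it does say what will be analysed.

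Most of this stands, and it limits the point to the overall acceptability statement. It does not remove the point, because P.5 says the questionnaire delivers this judgement and P.8 says the study will test it. A descriptive study still has to say what it describes.

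Three stronger readings are tempting, and the documents do not support them.

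- **Early stops lose unfavourable opinions and bias the survey upward.** P.9 says the questionnaire follows every enrollment, and the independent monitor checks that nurse interviews and data instruments are complete. Loss is possible but not shown.
- **The ambiguity is worth a stated number of percentage points.** Any such figure needs assumed answer counts and a composite definition that the plan does not contain.
- **The perception analysis is unspecified.** P.6 names the items to be reported and those to be coded.

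**Conclusion.** The point holds in limited form. The protocol claims an overall acceptability result that its instrument does not ask for and its analysis plan does not define. This affects one conclusion, the statement that the system is or is not acceptable for clinical use. It does not affect the planned item-by-item results, the P.2 aim, the problem-discovery rationale for 20 sessions, or the safety procedures in P.9.

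The missing early-stop summary is a reporting gap in P.6. It is not evidence that stops would be concealed, since the protocol collects them elsewhere.

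The conclusion rests on the wording of P.5, P.6, P.8 and P.9 alone and assumes no data. It should be corrected before further sessions, because the missing judgement cannot be obtained retrospectively from the answers. A misfilled endpoints heading alone would be editorial. It matters here because that is where the acceptability measure would be expected.

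**What to change.** 1. Add one 5-point agreement item to the questionnaire, on whether the system's performance was generally acceptable for clinical use. Replace the text under Study endpoints with the proportion of answers of 4 or 5 on that item. Report it descriptively beside Questions 1, 3A, 3C and 4A, with no pass/fail threshold. If the item is not wanted, delete the acceptability wording in P.5 and P.8 instead.
2. In P.6, report the number of early stops, who requested each (nurse, patient or family, where there was a request) and the reason. Use all started sessions as the denominator, and show this next to the survey results.

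**Cost.** One survey item, edits to P.5 and P.6 (or to P.5, P.6 and P.8 if the wording is deleted), and review of the revised questionnaire and protocol, since P.9 requires conduct to follow the protocol approved by the IRB and, if applicable, FDA. Sessions already completed, if any (the documents do not say), would lack the new item. The reported picture may be slightly less favourable.
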